#### **9.2.3.2 Studies 1245.110 and 1245.121**

Randomisation (Visit 2) follows screening (Visit 1) with no placebo run-in. During the randomised treatment period, visits are planned at Week 4, 12, 32, 52, and every 24 weeks thereafter. Starting at Week 22, phone calls are planned between the on-site visits to monitor safety. There will be a follow-up visit 30 days after treatment stop. Details can be found in the flow charts in CTPs [[c03946327](#), [c09098452](#)].

### **9.2.4 Study discontinuation**

Study discontinuation is not applicable for this meta-analysis. Study 1245.25 has been completed. See CTPs 1245.110 and 1245.121 for rules on study discontinuation [[c03946327](#), [c09098452](#), Section 3.3.4].

## **9.3       VARIABLES**

There are no confirmatory endpoints in this study. All variables in this meta-analysis will be analysed in an exploratory manner.

### **9.3.1      Exposures**

Exposure is defined as the time exposed to study medication (on-treatment approach; calculated as the difference between the date of last intake of study medication and the date of the first administration of the study medication plus 1 day) or the time under observation after starting randomised treatment (ITT approach; calculated as the difference between the date of last follow up and the date of the first administration of the study medication plus 1 day; also see SAP [[c16853237](#), Section 4.3.2.1]).

For incidence rate, the derivation of time at risk is as follows:

Patients with event:

time at risk in days = date of start of first event – treatment start date + 1

Patients without event:

time at risk in days = last date on treatment + 7 days\* (or last date in study for secondary analysis based on ITT approach) – treatment start date + 1

\* This is according to the definition of the residual effect period of 7 days as defined in the trial protocols for safety analyses for treatment-emergent events (also see SAP [[c16853237](#), Section 4.3].

### **9.3.2      Outcomes**

The objective of the meta-analysis is to evaluate the risk for LLA in an exploratory manner.

All outcome data, including recurrent events, are collected over the full trial period even after the first amputation event.

#### **9.3.2.1    Primary outcomes**

The primary outcomes are LLA events.

In studies 1245.110 and 1245.121, events leading to LLA are defined as AESIs in the protocols (see below). Specific information related to an LLA event (as a therapy) is to be recorded on dedicated eCRF pages. The specific information include: medical history of LLA, the date of each LLA event, the level (location) of the LLA event, and the medical reason leading to the LLA event.

A major LLA represents amputation above the ankle (below knee, knee, above knee). A minor LLA represents amputation at the ankle and below (ankle, tarsometatarsal, transmetatarsal and toes).

In study 1245.25, LLAs were not pre-specified in the protocol or specifically captured on eCRF pages, they were identified via a systematic search of SAE narratives, from events

reported as AEs, from those reported as a “medical procedure” under “concomitant therapy”, and from investigator comments describing the AEs. For details see SAP [[c16853237](#), Appendix 6.2].

Refer to [Sections 9.7.1](#) and [9.7.2](#) for the planned analyses.

*Definition and reporting of LLA events in the trial protocols (also see [Section 11.1](#)):*

In the protocols of the ongoing studies 1245.110 and 1245.121, events leading to LLA are defined as AESIs and include any event leading to a lower-limb procedure of amputation, auto-amputation, or disarticulation. Amputation is defined as a resection of a limb through a bone. Auto-amputation is a spontaneous separation of non-viable portion of the lower limb. Disarticulation is a resection of a limb through a joint. The following procedures are not included in the definition of events leading to LLA: debridement (removal of callus or dead tissue), procedures on a stump (such as stump revision, drainage of an abscess, wound revision, etc.), and other procedures (such as nail resection or removal) without a concomitant resection of a limb (amputation or disarticulation). The definitions are consistent with the 2015 guidance from the [REDACTED] (website: [REDACTED]).

Each lower-limb amputation, disarticulation, or auto-amputation should be reported separately. The SAE report for this type of AESI is to include the date of the procedure, the level of amputation or disarticulation, the medical condition(s) leading to the procedure, and if the patient had any of the known risk factor(s) for lower-limb amputation.

[figure not shown]
In the completed study 1245.25, events related to LLA were not defined as AESIs in the protocol, but were identified via a systematic search of the study database (see above).

### 9.3.2.2 Secondary outcomes

The secondary outcomes are AEs related to amputation.

A search with a pre-defined list of MedDRA PTs will be performed to identify all AEs related to amputation. These AEs include vascular disorders, diabetic-foot-related events, wound/infections, nervous system disorders, and volume depletion events. For the list of preferred terms for preceding/related events see SAP [[c16853237](#), Appendix 6.1]. The occurrences of these AEs do not necessarily lead to amputation procedures.

Refer to [Sections 9.7.1](#) and [9.7.2](#) for the planned analyses.

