### **9.2.2.2 Studies 1245.110 and 1245.121**

Study 1245.110 will include patients with chronic heart failure with preserved ejection fraction. Study 1245.121 will include patients with chronic heart failure with reduced ejection fraction. Detailed eligibility criteria can be found in CTPs [[c03946327](#), [c09098452](#), Section 3.3] and the key criteria are summarised below.

The key inclusion criteria are:

- Age  $\geq 18$  years (Japan, age  $\geq 20$  years)
- Chronic HF NYHA class II to IV
- Ejection fraction (EF) and NT-proBNP criteria

- 1245.110: preserved EF (LVEF >40%) and elevated NT-proBNP (>300 pg/ml; >900 pg/ml for patients with atrial fibrillation)
- 1245.121: reduced EF (LVEF ≤40%) and elevated NT-proBNP (≥2500 pg/ml if EF 36 to 40%, ≥1000 pg/ml if EF 31 to 35%, ≥600 pg/ml if EF ≤30% or if EF ≤40% with documented hospitalisation for HF within 12 months prior to screening; for patients with atrial fibrillation, double the level of NT-proBNP is applied for each EF category)
- 1245.110 only: structural heart disease within 6 months or documented hospitalisation for HF within 12 months prior to screening
- 1245.121 only: stable dose of medical therapy for HF consistent with local and international cardiology guidelines

The key exclusion criteria are:

- Myocardial infarction, coronary artery bypass graft surgery or other major cardiovascular surgery, stroke or transient ischaemic attack ≤90 days before screening
- Heart transplant recipient, or listed for heart transplant
- Acute decompensated HF
- SBP ≥180 mmHg at randomisation
- Symptomatic hypotension and/or SBP <100 mmHg at screening or randomisation
- Impaired renal function defined as eGFR (CKD-EPI)cr <20 ml/min/1.73 m^2 or requiring dialysis at screening

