4.1.2 Secondary Outcomes: Adverse Events Related to Amputation

The term “adverse events related to amputation” is used for events generally known to be related and often preceding amputations. The occurrence of these types of events not necessarily leads to amputation procedures.

[Appendix 6.1](#) contains a list of preferred terms for selecting AEs related to amputation. This list will be reviewed before the conduct of the analysis to ensure that all the PTs are still current in the latest MedDRA version used for the analysis.

This endpoint will be analysed for all patients and for the subset of patients with amputations.

See [Section 4.3.2.2.2](#) for details about the planned analysis.

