6 APPENDIX

6.1 LIST OF PREFERRED TERMS FOR PRECEDING/RELATED EVENTS

Vascular AEs

Angiopathy

Arterial bypass operation

Arterial disorder

Arterial graft

Arterial occlusive disease

Arterial stenosis

Arterial stent insertion

Arteriosclerosis

Arterial thrombosis

Arterial therapeutic procedure

Diabetic microangiopathy

Diabetic vascular disorder

Femoral artery occlusion

Iliac artery occlusion

Intermittent claudication

Ischaemic limb pain

Microangiopathy

PAOD Peripheral arterial occlusive disease

Peripheral ischaemia

Peripheral coldness

Peripheral artery stenosis

Peripheral artery restenosis
Peripheral artery occlusion
Peripheral artery thrombosis
Peripheral vascular disorder
Peripheral ischaemia
Peripheral arterial re-occlusion
Peripheral vascular disorder
Poor peripheral circulation
Peripheral artery angioplasty
Peripheral endarterectomy
Peripheral artery bypass
Peripheral artery stent insertion
Spontaneous amputation
Thrombosis

Diabetic foot related AEs

Atherosclerotic gangrene

Bone abscess

Diabetic foot

Diabetic foot infection

Diabetic gangrene

Diabetic neuropathic ulcer

Diabetic ulcer

Dry gangrene

Cellulitis enterococcal

Cellulitis staphylococcal

Cellulitis streptococcal

Cellulitis gangrenous

Extremity necrosis

Gangrene

Infections Cellulitis

Infected skin ulcer

Infected skin ulcer

Ischaemic ulcer

Localised infection

Necrosis ischaemic

Neuropathic ulcer

Osteitis

Osteomyelitis

Osteomyelitis acute

Osteomyelitis bacterial
Osteomyelitis chronic
Osteomyelitis fungal
Osteomyelitis salmonella
Osteonecrosis
Penetrating atherosclerotic ulcer
Post-operative wound infection
Skin erosion
Skin ulcer
Staphylococcal osteomyelitis
Soft tissue infection
Subperiosteal abscess

Wound/Infection

Abscess limb

Burn infection

Impaired healing

Wound

Skin wound

Skin infection

Subcutaneous abscess

Vasculitic ulcer

Wound abscess

Wound complication

Wound dehiscence

Wound infection

Wound infection bacterial

Wound infection fungal

Wound infection staphylococcal

Wound infection pseudomonas

Wound necrosis

Wound sepsis

Wound treatment

Nervous System Disorders

Areflexia

Autonomic neuropathy

Burning sensation

Diabetic neuropathy

Hypoesthesia

Neuropathy peripheral

Paraesthesia

Peripheral sensory neuropathy

Peripheral sensorimotor neuropathy

Sensory disturbance

Volume depletion

Hypovolaemia

Dehydration

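### The fixed preferred-term list that defines AEs related to amputation has thrombosis, occlusion and ischaemia terms but no embolism term, and its planned review would not reveal the gap

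*Protocol*

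**What the plan says.** Protocol 9.3.2.2 sets out how the secondary outcome is found: "A search with a pre-defined list of MedDRA PTs will be performed to identify all AEs related to amputation". SAP 4.1.2 states that Appendix 6.1 "contains a list of preferred terms for selecting AEs related to amputation", and neither document gives another route into the outcome. SAP 4.3.2.2.2 uses the same term groups for the analysis of events preceding an amputation.

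The vascular group in Appendix 6.1 includes "Peripheral artery thrombosis" and "Femoral artery occlusion". One review of the list is planned: "This list will be reviewed before the conduct of the analysis to ensure that all the PTs are still current in the latest MedDRA version".

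In the two heart failure trials (Protocol 9.3.2.1), "events leading to LLA are defined as AESIs and include any event leading to a lower-limb procedure of amputation, auto-amputation, or disarticulation". Each such report is to name the medical condition that led to the procedure. These events are adverse events of special interest (AESIs).

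The heart failure trials also admit patients with atrial fibrillation. For 1245.121, Protocol 9.2.2.2 states that "for patients with atrial fibrillation, double the level of NT-proBNP is applied for each EF category", and 1245.110 has its own threshold for these patients.

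**The concern.** The list reaches widely for arterial trouble in the limb. It takes in *Peripheral coldness*, *Arteriosclerosis* and the unspecific *Thrombosis*. Against that breadth, the absence of any embolism term looks like an omission, and no reason is given for it.

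That an embolus can block a leg artery, and that atrial fibrillation favours this, is general clinical knowledge and not something the documents state. I use it only to explain why the missing term is worth attention in these populations.

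At stake are the vascular-AE frequencies, incidence rates and Cox model, the secondary outcome as a whole, and the tables of AEs preceding an amputation. In 1245.110 and 1245.121 the plan collects the very information that would show whether the list is complete, namely the events reported as leading to LLA, but no step compares the two.

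**Working it through.** **Step 1. Is there another way into the secondary outcome?** Protocol 9.3.2.2 and 9.7.2.1 and SAP 4.1.2 and 4.3.2.2.2 were read together. All of them rest on Appendix 6.1. None adds an AESI leading to LLA, or its preferred term, to the outcome or to the preceding-AE analysis.

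**Step 2. What does the list contain?** Appendix 6.1 was transcribed and searched by word stem.

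| Group | Entries |
|---|---|
| Vascular | 35 |
| Diabetic foot | 36 |
| Wound/infection | 19 |
| Nervous system | 10 |
| Volume depletion | 2 |
| Total | 35 + 36 + 19 + 10 + 2 = 102 |

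Three terms appear twice (*Peripheral ischaemia*, *Peripheral vascular disorder*, *Infected skin ulcer*), so 102 − 3 = 99 are distinct.

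| Stem | Distinct terms | Terms |
|---|---|---|
| thromb | 3 | Arterial thrombosis; Peripheral artery thrombosis; Thrombosis |
| occlu | 6 | Arterial occlusive disease; Femoral artery occlusion; Iliac artery occlusion; Peripheral arterial occlusive disease (entered with the prefix PAOD); Peripheral artery occlusion; Peripheral arterial re-occlusion |
| ischaem | 4 | Peripheral ischaemia; Ischaemic limb pain; Ischaemic ulcer; Necrosis ischaemic |
| embol | 0 | none |

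**Step 3. Would the planned review catch this?** No. A check that each listed term is still valid cannot find a term that was never listed.

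**Step 4. Which analyses are touched?**
- *Touched, in all three studies:* the vascular-AE group, the secondary outcome and the preceding-AE tables. The condition is that the event carries an embolism term and no listed term. An episode that also carries *Extremity necrosis* or *Gangrene* enters the secondary outcome through the diabetic-foot group but still not the vascular group.
- *Not touched:* the primary outcome, which counts an LLA whatever its cause (Protocol 9.3.2.1; SAP Appendix 6.2 for 1245.25), and the SAF-M2 table of reasons for LLA (SAP 4.3.2.2.1).

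**Step 5. How large could the effect be?** The documents give no embolic event counts, so only a scenario is possible. Let q be the placebo-arm share of patients with a vascular event whose only vascular coding is an embolism term. Let h be the hazard ratio (HR) for those events, with HR 1 for all other vascular events. Both q and h are assumptions.
- The HR for all vascular events is about (1 − q) + q·h, while the current list would show about 1.0.
- If instead the effect is the same for all vascular events, the HR is not biased, and its standard error grows by 1/√(1 − q).

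| q | All-vascular HR at h = 2 | Standard error factor |
|---|---|---|
| 0.05 | 0.95 + 0.10 = 1.05 | 1/√0.95 = 1.026 |
| 0.10 | 0.90 + 0.20 = 1.10 | 1/√0.90 = 1.054 |
| 0.20 | 0.80 + 0.40 = 1.20 | 1/√0.80 = 1.118 |

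These are illustrations for the vascular group alone. For the whole secondary outcome the missed share can be expected to be smaller, since a patient counts with any listed term from any of five groups.

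**The case against.** The strongest reply is that little is lost. An embolic episode in a leg is likely also to be reported under a listed term such as *Peripheral ischaemia*, *Peripheral artery occlusion* or *Arterial thrombosis*. The analysis is exploratory with no confirmatory endpoints (Protocol 9.3), and the same list applies to both arms of double-blind trials. All of this stands. It limits the size of the problem but gives no reason to leave the terms out.

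Four stronger readings are tempting, and the documents do not support them:

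- *The plan ignores the events that led to an LLA.* It does not. The LLA counts in the primary outcome whatever its cause, and SAF-M2 tabulates the reasons. SAP 4.3.2.2.1 also tabulates patients with LLA by system organ class and preferred term. Because SAP Appendix 6.2 treats amputation as a procedure and not an AE in itself, that table probably shows the AE behind the amputation. None of these tables feeds the secondary outcome, however.
- *The gap belongs to the heart failure trials, so half of SAF-M1 is affected.* These trials supply about 4126 + 2850 = 6976 of 7020 + 6976 = 13,996 patients. Not all of them have atrial fibrillation, and the documents give no prevalence. The list applies equally to 1245.25, whose summarised key criteria do not exclude atrial fibrillation.
- *Every amputee whose leading event is off the list appears with no preceding related AE.* This does not follow. The analysis counts patients with any listed AE before the amputation, so an earlier skin ulcer or cellulitis is enough. If the list covered 80 to 95% of leading events, 5 to 20% of amputees would be only an upper bound on those shown with none.
- *Every AESI leading to LLA should count as a preceding related AE.* That would push the SAF-M2 frequency towards 100% by construction. It would also bring in trauma and tumour, which the SAP sets aside in some SAF-M2 tables. SAP 4.1.2 describes the outcome as events generally known to be related to amputation, which is narrower than whatever preceded one.

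**Conclusion.** The point holds in a limited form. A list intended to find all AEs related to amputation has no embolism term, and the planned review cannot detect that. Limb arterial events coded solely to an embolism term are missed in the vascular group, the secondary outcome and the preceding-AE tables of all three studies. The primary outcome stands as planned.

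The size is unknown and may be small. A shifted vascular HR requires both that such events are a noticeable share and that their treatment effect differs from that on other vascular events. Otherwise the cost is some precision and a modest undercount. The conclusion assumes that embolism events are coded to preferred terms of their own in the MedDRA version used, which the sponsor can confirm.

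**What to change.** 1. In SAP Appendix 6.1, add to the vascular group the current MedDRA preferred terms for peripheral or limb artery embolism and for unspecified arterial embolism. Apply them to all three studies. Do this before 1245.110 and 1245.121 are unblinded. Protocol Section 6 expects the first database lock in Q3 2020, and the plan is dated April 2019. As 1245.25 is already complete, choose the terms by their meaning and not by its counts per arm.
2. In SAP 4.1.2, extend the list review from currency to completeness. Compare the list, blinded to treatment, with the preferred terms of AESIs reported as leading to LLA in the two heart failure trials, excluding trauma and tumour. List the terms that are not in Appendix 6.1.
3. Do not count every such AESI automatically as a preceding related AE.

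The cost is a few added terms and one blinded listing, on data already collected. The drawback is that the list will differ slightly from the one in the current plan. Results with the current Appendix 6.1 list can be shown alongside.

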### 9.3.3 Covariates

Covariates such as demographics (sex, race, geographical region, age), baseline medical conditions (renal function, hypertension, diabetes, peripheral arterial occlusive disease, diabetic foot, coronary artery disease, diabetic neuropathy, diabetic retinopathy, history of lower-limb amputation, osteomyelitis, gangrene, nephropathy, HF at baseline, smoking

Proprietary confidential information © 2019 Boehringer Ingelheim International GmbH or one or more of its affiliated companies

status; for patients with diabetes: HbA1c), and baseline therapies (diuretics, loop diuretics, anticoagulants, anti-platelets; for patients with diabetes: insulin, metformin, sulphonyl urea) will be investigated in subgroup analyses of the LLA events and AEs related to amputation.

In addition, further demographic and baseline variables will be descriptively summarised (i.e. ethnicity, BMI, weight, time since diagnosis of diabetes, blood pressure).

All demographic and baseline variables with categories are shown in Table 9.3.3: 1 (also see the SAP [[c16853237](#), Table 4.3: 2]).

Table 9.3.3: 1 Demographic and baseline variables with categories

Variable	Demographics/Baseline characteristics Categories
Sex	Male Female
Race	White Black/African Asian Hawaiian/Pacific Islander Amer. Ind./ Alaska Nat.
Ethnicity	Hispanic/Latino Not Hispanic/Latino
Geographical region &	Europe Africa/Middle East North America Latin America Asia Other (if any)
Age (years) categories	Version 1 <65 65 to <75 75 to <85 ≥85  Version 2 <65 65 to <75 ≥75
	(Decision will be taken on which version to use based on the size of the elderly population group ≥85 years of age)
BMI (kg/m  )	<25 25 to <30 30 to <35 ≥35
Weight (kg)	≤70 >70 to ≤80 >80 to ≤90 >90

To be continued

Table 9.3.3: 1 Demographic and baseline variables with categories (continued)

Variable	Demographics/Baseline characteristics	
	Categories	
Smoking status	Never smoked	
	Ex-smoker	
	Currently smokes	
Time since diagnosis of diabetes	Version 1 for SAF-M1 pool: ≤1 year >1 year to 5 years >5 years to 10 years >10 years Not applicable (as no diabetes diagnosed)	Version 2 for SAF-M2 pool: ≤1 year >1 year to 5 years >5 years to 10 years >10 years to 20 years >20 years Not applicable (as no diabetes diagnosed)
Baseline HbA 1c (%)	Version 1 <8.5 ≥8.5	Version 2 <8 8 to <9 (for diabetic patients only)
Blood pressure (mmHg)	≥130/80 <130/80 (controlled)*	
Renal function (eGFR) (CKD-Epi) (mL/min/1.73m  )	<30 30 to <45 45 to <60 60 to <90 ≥90	
Insulin use	Yes/No	
Metformin use	Yes/No	
Sulphonyl urea use	Yes/No	
Loop diuretics	Yes/No	
Diuretics	Yes/No	
Anticoagulant use	Yes/No	
Anti-platelet use	Yes/No	
Hypertension	Yes/No	
Diabetes	T1DM T2DM No Diabetes	
Peripheral arterial occlusive disease	Yes/No	
Diabetic foot at baseline	Yes/No	
Coronary artery disease	Yes/No	

To be continued

Table 9.3.3: 1 Demographic and baseline variables with categories (continued)

Variable	Demographics/Baseline characteristics
	Categories
Diabetic neuropathy	Yes/No
Diabetic retinopathy	Yes/No
History of lower limb amputation	Yes/No
Osteomyelitis	Yes/No
Gangrene	Yes/No
Nephropathy	Yes/No
Heart failure at baseline	Yes/No

\* Patients must have both SBP below 130 and DBP below 80 to be considered controlled.

& Australia included in North America and South Africa included in Africa/Middle East.

All subgroup variables with categories are shown in [Table 9.3.3: 2](#) (also see the SAP [\[c16853237\]](#), Table 4.3: 3).

Table 9.3.3: 2 Subgroup variables and categories

Variable	Subgroup Analysis Categories
Sex	Male Female
Race	White Black/African Asian Other
Geographical region	Europe Africa/Middle East North America Latin America Asia Other (if any)
Age (years) categories	Version 1 <65 65 to <75 75 to <85 ≥85 or Version 2 <65 65 to <75 ≥75 In case of low number of events for patients ≥85
Renal function (eGFR) (CKD-Epi) (mL/min/1.73m  )	<30 30 to <45 45 to <60 60 to <90 ≥90
Insulin use	Yes/No (Diabetic patients only)
Metformin use	Yes/No (Diabetic patients only)
Sulphonyl ureas use	Yes/No (Diabetic patients only)
Loop diuretics	Yes/No
Baseline HbA 1c (%)	<8.0, ≥8.0
Baseline HbA 1c (%)	<8.5, ≥8.5
Anticoagulant use	Yes/No
Anti-platelets use	Yes/No
Diuretics	Yes/No
Hypertension	Yes/No
Diabetes	T1DM T2DM No Diabetes (Diabetes yes/no if number of events too low)

To be continued

Table 9.3.3: 2 Subgroup variables and categories (continued)

Variable	Subgroup Analysis Categories
Peripheral arterial occlusive disease	Yes/No
Diabetic foot at baseline	Yes/No (Diabetic patients only)
Coronary artery disease	Yes/No
Diabetic neuropathy	Yes/No
Diabetic retinopathy	Yes/No (Diabetic patients only)
History of lower limb amputation	Yes/No
Osteomyelitis	Yes/No
Gangrene	Yes/No
Nephropathy	Yes/No
HF at baseline	Yes/No
Smoking status	current smoker ex-smoker never smoked

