**1245.110 (EMPEROR-Preserved) and 1245.121 (EMPEROR-Reduced), both ongoing**

**Aim:** To investigate the safety and efficacy of empagliflozin versus placebo on top of guideline-directed medical therapy in patients with heart failure with reduced or preserved ejection fraction

**Population:** T2D and non-T2D, age ≥18 years, chronic HF (NYHA II–IV)

Figure 9.1: 1 Design of studies 1245.25, 1245.110, and 1245.121

QD/qd, once daily; T2DM, type 2 diabetes mellitus; LVEF, left ventricular ejection fraction; SoC, standard of care

\* Guideline-directed therapies

This meta-analysis will be exploratory. All analyses will be based on the treated set, which includes all patients treated with at least 1 dose of study medication (as randomised). Due to the different patient eligibility criteria (see [Section 9.2.2](#)) and methods in capturing LLA and related events (see [Section 9.3.2.1](#)), two analysis groupings will be used in the meta-analysis. SAF-M1 includes all 3 studies while SAF-M2 includes studies 1245.110 and 1245.121. All

analyses will be carried out separately for each SAF and for each study, unless otherwise indicated in [Section 9.7.1](#) and [9.7.2](#).

The primary outcomes are LLA events (see [Section 9.3.2.1](#)).

LLA events will be analysed using frequency analyses, incidence rates, Kaplan-Meier estimates, and Cox proportional hazards models to compare empagliflozin with placebo. For SAF-M2, where additional information on LLA events are collected on the eCRF, the reasons leading to LLA, the number of LLA episodes, level of LLA, etc., will be summarised.

As the primary analysis, the “on-treatment” approach will include events with an onset date within the treatment period (from first to last dose of study medication plus 7 days to account for the residual drug effect). An ITT approach will be used as a secondary analysis, which includes all events during the observation period after starting randomised treatment, regardless if the patient was taking study medication or not when the event occurred.

Since deaths are competing events to amputations, a competing risk analysis considering all-cause death and a cumulative incidence analysis will be carried out.

Subgroups by demographics, baseline medical conditions, and baseline therapies will be analysed for LLA events for SAF-M1 and SAF-M2 (see [Section 9.3.3](#) for subgroup variables).

The secondary outcomes are AEs related to amputation (see [Section 9.3.2.2](#)).

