### **9.7.1 Main analysis**

LLA events (primary outcome) and AEs related to amputation (secondary outcome) will be analysed using frequency analyses, incidence rates, Kaplan-Meier estimates, and Cox proportional hazards models to compare empagliflozin with placebo in the pooled populations of SAF-M1, SAF-M2, and for each of the 3 studies (1245.25, 1245.110, and 1245.121) separately. Kaplan-Meier analyses (cumulative incidence functions) for time to first event will be provided by treatment and stratified by study.

Cox proportional hazards models will include the factors study, diabetes mellitus status (T1DM, T2DM, no diabetes), and treatment (all empa vs placebo).

As the primary analysis, the “on-treatment” approach will include events with an onset date within the treatment period (from first to last dose of study medication plus 7 days to account for the residual drug effect).

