#### 9.7.2.3 Subgroup analysis

All subgroup variables with categories are shown in [Table 9.3.3: 2](#). Subgroup analyses for SAF-M1 and SAF-M2 will be provided for frequency and incidence rate tables, KM analyses, and for Cox models. Subgroup analyses will be performed for LLA events and AEs related to amputation.

For Cox models for time to first event analysis, the following factors will be included in the model: study, treatment, <subgroup>, treatment-by-<subgroup> interaction.

For time-to-event endpoints, at a minimum, a count of events will be provided, and if sample size is statistically sufficient, i.e. 14 patients with events in total over the 2 treatment groups for each subgroup category, a statistical analysis using the Cox regression model will be performed. If the affected category is too small (<14 patients with events), the category may be only described descriptively and no inferential analysis is performed, or the category may be pooled with another category if this is justifiable from a scientific perspective.

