4.3.2.3 Subgroup analyses

Subgroup analyses will be performed for the subgroups displayed in [Table 4.3: 3](#). Subgroup analyses for SAF-M1 and SAF-M2 will be provided for frequency and incidence rate tables, KM analyses and for Cox models. Subgroup analyses will be performed for amputation events as well as for the adverse events related to amputations analysis.

For Cox models for time to first event analysis the following factors will be included in the model: study, treatment, <subgroup>, treatment by <subgroup> interaction.

For time-to-event endpoints, at a minimum, a count of events will be provided, and if sample size is statistically sufficient, i.e. 14 patients with events in total over the 2 treatment groups for each subgroup category, a statistical analysis using the Cox regression model will be performed. If otherwise the affected category is too small (<14 patients with events) a category may be only described descriptively and no inferential analysis is performed, or the category might be pooled with another category if this is justifiable from a scientific perspective.

Table 4.3: 3 Subgroup analyses

Variable	Subgroup Analysis Categories
Sex	Male Female
Race	White Black/African Asian Other
Geographical region	Europe Africa/Middle East North America Latin America Asia Other (if any)
Age (years) categories	Version 1 < 65 65 to < 75 75 to < 85 ≥ 85 or

	< 65
	65 to < 75
	= 75
	In case of low number of events for patients >= 85
Renal function (eGFR) (CKD-Epi) (mL/min/1.73m ²)	<30 30 to < 45 45 to <60 60 to <90 ≥90
Insulin use	Yes/No (Diabetic patients only)
Metformin use	Yes/No (Diabetic patients only)
SU use	Yes/No (Diabetic patients only)
Loop diuretics	Yes/No
Baseline HbA _{1c} (%)	<8.0, >=8.0
Baseline HbA _{1c} (%)	<8.5, >=8.5
Anticoagulant use	Yes/No
Anti-platelet use	Yes/No
Diuretics	Yes/No
Hypertension	Yes/No
Diabetes	T1DM T2DM No Diabetes (Diabetes yes/no if number of events to low)
Peripheral arterial occlusive disease	Yes/No
Diabetic foot at baseline	Yes/No (Diabetic patients only)
Coronary artery disease	Yes/No
Diabetic neuropathy	Yes/No
Diabetic retinopathy	Yes/No (Diabetic patients only)
History of lower limb amputation	Yes/No
Osteomyelitis	Yes/No
Gangrene	Yes/No
Nephropathy	Yes/No
HF at baseline	Yes/No
Smoking status	current smoker ex-smoker never smoked

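### The diabetic neuropathy subgroup is not limited to diabetic patients, unlike diabetic foot and retinopathy, so its No level is mixed by diabetes status

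*Protocol*

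**What the plan says.** Protocol Section 9.3.3, Table 9.3.3: 2 lists the subgroup variables. Two of the three diabetic complications carry a restriction: "Diabetic foot at baseline Yes/No (Diabetic patients only" and "Diabetic retinopathy Yes/No (Diabetic patients only". The third does not: "Diabetic neuropathy Yes/No". SAP Section 4.3.2.3, Table 4.3: 3 has the same three rows with the same difference.

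The neuropathy wording also occurs in the descriptive Table 9.3.3: 1. There all three complications are unrestricted, which is harmless for a baseline summary. The point concerns the subgroup tables only.

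The running text of Section 9.3.3 limits HbA1c and the antidiabetic drugs to patients with diabetes ("for patients with diabetes: insulin, metformin, sulphonyl urea"), but says nothing of the kind for neuropathy.

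The design figure in protocol Section 9.1 gives the population of the two heart failure studies as "T2D and non-T2D, age ≥18 years, chronic HF (NYHA II–IV". Both studies are in SAF-M1 and SAF-M2, the two pools for which subgroup analyses are planned.

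The subgroup Cox model contains "study, treatment, <subgroup>, treatment-by-<subgroup> interaction" (protocol Section 9.7.2.3); SAP Section 4.3.2.3 lists the same terms. The main model differs: "Cox proportional hazards models will include the factors study, diabetes mellitus status (T1DM, T2DM, no diabetes), and treatment (all empa vs placebo".

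**The concern.** A patient without diabetes cannot have diabetic neuropathy. Every Yes patient is therefore diabetic, while No holds two different groups: diabetic patients without neuropathy, and all non-diabetic heart failure patients. Comparing Yes with No then compares diabetes status as well as neuropathy. The study factor does not remove this, because the mixing happens within 1245.110 and 1245.121.

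Neuropathy is one of the baseline conditions that the plan examines for amputation risk, and protocol Section 9.9 relies on the subgroup analyses to judge how differences between the populations affect the results. A neuropathy contrast that carries a diabetes contrast inside it serves that purpose poorly.

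**Working it through.** **Text comparison.**

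| Row in the subgroup tables | Restricted in the table? | Restricted in the text of 9.3.3? |
|---|---|---|
| Insulin, metformin, sulphonyl urea | yes | yes |
| HbA1c (two rows) | no | yes |
| Diabetic foot | yes | no |
| Diabetic retinopathy | yes | no |
| Diabetic neuropathy | **no** | **no** |

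Among the rows that presuppose diabetes, neuropathy is the only one restricted in neither place. Followed literally, the plan puts every non-diabetic patient into No.

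**What this affects.**

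1. Frequencies, incidence rates, Kaplan-Meier curves and the subgroup main effect: the No level reflects the diabetes mix, whatever the treatment effect is.
2. The treatment-by-neuropathy interaction: the HR in No is roughly an event-weighted average of the HRs in its two components. If those HRs are equal, mixing does not move it. If they differ, it does.

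**Sizes from the documents** (protocol Section 9.5). 1245.25 has 7020 treated patients, all with T2DM by its inclusion criteria. The heart failure studies plan 4126 + 2850 = 6976. The total is 13,996, in line with the approx. 14 000 in the protocol; 6976/13,996 = 49.8% come from the heart failure studies.

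**Assumed inputs** (the documents give none of these):

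- p, share of heart failure patients with diabetes: 40 to 50%
- q, share of diabetic patients with neuropathy: 30% (20 to 40% for the patient shares)
- r, LLA rate in diabetic relative to non-diabetic patients: 3 to 5
- HR 1.5 in all diabetic patients whatever their neuropathy status, and 1.0 in non-diabetic patients

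**Patient share.** Let n0 = 6976(1 − p) be the non-diabetic patients, and n1 the diabetic patients without neuropathy: 6976·p(1 − q) in SAF-M2 and (7020 + 6976·p)(1 − q) in SAF-M1. The non-diabetic share of No is n0/(n0 + n1). Over q = 20 to 40% it is 56 to 71% in SAF-M2 and 29 to 42% in SAF-M1.

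**HR in No.** The event share of non-diabetic patients is e = n0/(n0 + r·n1), and the averaged HR is 1.0·e + 1.5·(1 − e). With q = 30%:

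| Pool | p | n0 | n1 | e (r = 3) | HR in No | e (r = 5) | HR in No |
|---|---|---|---|---|---|---|---|
| SAF-M2 | 40% | 4186 | 1953 | 0.417 | 1.29 | 0.300 | 1.35 |
| SAF-M2 | 50% | 3488 | 2442 | 0.323 | 1.34 | 0.222 | 1.39 |
| SAF-M1 | 40% | 4186 | 6867 | 0.169 | 1.42 | 0.109 | 1.45 |
| SAF-M1 | 50% | 3488 | 7356 | 0.136 | 1.43 | 0.087 | 1.46 |

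The HR in Yes is 1.5 throughout. The false ratio of HRs (Yes to No) is therefore 1.5/1.39 to 1.5/1.29, or 1.08 to 1.16, in SAF-M2, and 1.5/1.46 to 1.5/1.42, or 1.03 to 1.06, in SAF-M1. Averaging log HRs instead gives 1.27 to 1.37 and 1.40 to 1.45 in No, which leads to the same conclusion.

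**Wider assumptions.** With 30 to 70% of heart failure patients non-diabetic, 10 to 30% neuropathy, r from 3 to 10, and log averaging, the false ratio is 1.02 to 1.24 in SAF-M2 and 1.01 to 1.09 in SAF-M1.

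**After restriction to diabetic patients**, the non-diabetic share of No is 0% and the ratio is 1.00.

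**The case against.** - **The interaction may be undisturbed.** A reader might infer that the interaction test measures diabetes in any event. The documents do not support that: it requires a treatment effect that differs by diabetes status, and nothing in them suggests one. Within No, empagliflozin versus placebo is still a comparison of randomised groups. This stands, and it limits the point. It does not rescue the rates, curves and main effect.
- **Diabetes has its own row.** A reader might also infer that a diabetes difference would go unseen and be reported as a neuropathy effect. Diabetes is itself a subgroup variable in the same tables, subject to the same rule of 14 patients with events, so such a difference would normally be visible beside the neuropathy result. That helps a reader notice the problem; it does not correct the neuropathy estimate.
- **The distortion is small against sampling error.** Assume 100 events per level, split evenly between arms. The SE of the log ratio of HRs is then √(4/100 + 4/100) = 0.28, whereas ln(1.5/1.29) = 0.15, about half an SE. The documents give no event counts. This stands for the interaction.
- **It may be a missing label, not a decision.** The table labels are not exhaustive, as the HbA1c rows show. The documents do not show that including non-diabetic patients was intended. For HbA1c, though, the text supplies the restriction; for neuropathy nothing does, and the two documents agree on the unrestricted row.

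**Conclusion.** The inconsistency is real and appears in both documents. As written, the neuropathy comparison is confounded by diabetes status in its frequencies, rates, Kaplan-Meier curves and main effect. Its interaction with treatment is distorted if, and only if, the treatment effect differs by diabetes status.

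Under the narrower set of assumptions the distortion would be modest in SAF-M2 and slight in SAF-M1, where 1245.25 adds 7020 diabetic patients. The sizes rest on assumed prevalences, rate ratio and HRs, so they illustrate the mechanism and do not predict the result.

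The analysis is exploratory and this is one subgroup among many; the primary result does not depend on it. It is a minor point, worth making because the repair is so cheap.

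**What to change.** Add the label (Diabetic patients only) to the diabetic neuropathy row in protocol Table 9.3.3: 2 and SAP Table 4.3: 3, as already done for foot and retinopathy. If the row was left open on purpose, say why in one sentence.

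The change needs no new data and alters no other analysis. Its cost is that non-diabetic patients, and whatever LLA events they have (few, if amputation is rarer without diabetes), leave that one subgroup analysis. They remain in the main analysis and in the diabetes subgroup.
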